### 8.1 Baseline Demographics

Patient characteristics will be summarized by treatment. Refer to the table of baseline characteristics (tables 6 -12, Section 8.9.3)

### 8.2 Primary End Point Analysis

The primary endpoint is the absolute walking distance (AWD) measured by treadmill test at 3 months.

The measured absolute walking distance, by treatment group and time point, will be presented for all patients within the ITT population in a summary table (Table 16, Section 8.9.5).

The primary analysis will estimate the difference in the absolute walking distance at 3 months between the two treatment groups (NMES + local available exercise therapy vs. local available exercise therapy only) by using a

Tobit regression model to address the cut-off point of 15 min (where the distance reached to this point will be censored at 790 metres). The model will include the measurements of AWD baseline, treatment indicator, centre indicator and group indicator as covariates. The results of the Tobit regression model will be reported (see Table 17, Section 8.9.5).

As a secondary analysis of the primary endpoint, we will estimate the difference between the groups in the proportion of patients that increased the absolute walking distance at 3 months by 60 metres or more from baseline using a chi-square test (Table 18). This analysis will be repeated for the proportion of patients that increases the AWD at 3 months by 100 metres or more (Table 19).

A summary table of proportion of patients who increased the AWD both by more than 60 and by more than 100 metres by treatment and by visit will be presented (Table 20 and Table 21)

A Multilevel Tobit model will be used to investigate the difference in absolute walking distance between the two treatment groups at 3, 6 and 12 months adjusting for the following independent baseline covariates:

- AWD baseline measurement
- Treatment
- Time
- Time\*Treatment interaction,
- Centre
- Group (SET vs non-SET)
- Age
- Gender
- BMI
- Smoking Status

The results of the Multilevel Tobit model will be presented (Table 22, Section 8.9.5)

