## 5.9 Randomization

Once eligibility has been confirmed, subjects will be randomised to one of the two arms of the study and assigned a pseudonymised study number unique to each individual enrolled in the trial.

Randomisation will take place via the InForm system (the electronic case report form database for the study), which will be programmed with a randomisation schedule provided by an independent statistician. Randomisation will be blocked with random block sizes and stratified by centre.

SET CENTRE randomisation:

- Control 1: EA + SET
- Treatment 1: EA + SET + NMES

Non-SET CENTRE randomisation:

- Control 2: EA
- Treatment 2: EA + NMES

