### **7.3 Primary Endpoint variable**

Absolute walking distances (AWD) at baseline, 3, 6 and 12 months (measured in metres).

For participants who walked more than 15 minutes on the treadmill during any follow up, their AWD will be censored at 790 metres. It was communicated directly to the sites that 790 metres will be used as a censored value.

In cases that the AWD is recorded when the patient walked more than 15 minutes during the study assessment (at baseline) the patient will be removed from the analysis.

In cases that the AWD is recorded at 3, 6 or 12 months with a value equal to or greater than 790 metres the value will then be censored at 790m.

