### **8.4 Subgroup Analysis**

The subgroups are described in section 6.3. Summary statistics for the subgroups are presented (Section 8.9.7.1 and Section 8.9.7.2).

Subgroup analysis will investigate the effect of the intervention among subgroups. The subgroup effects will be based on the interaction between subgroup and treatment through a set of Tobit regression models. Tobit Regression will be used to evaluate the difference in absolute walking distance at 3 months between treatment groups. The Tobit model will include the AWD baseline measurement, a treatment indicator, a centre indicator and a group indicator (SET vs non-SET) as covariates . The results of the Tobit regression model will be reported (see Section 8.9.7.3).

In addition, as secondary analysis we will estimate both the difference between the proportion of patients whose absolute walking distance at 3 months improved by 60 metres or more from baseline and the difference between the proportion of patients whose absolute walking distance at 3 months improved by 100 metres or more from baseline using a chi-square test.

The secondary analysis will be repeated for each one of the subgroups.

All subgroup analyses will be presented in a Forest plot for comparison (see Figure 5).

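### The 60 m and 100 m walking-distance responder comparisons rest on an unadjusted chi-square test, which is valid but somewhat inefficient and gives no effect estimate

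*SAP*

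**What the plan says.** SAP 8.2 sets the responder comparison beneath the primary Tobit analysis, as a secondary look at the same endpoint. It undertakes to estimate the between-arm difference in the proportion of patients that "increased the absolute walking distance at 3 months by 60 metres or more from baseline using a chi-square test". It then adds: "This analysis will be repeated for the proportion of patients that increases the AWD at 3 months by 100 metres or more". Table 2 lists the same tests with no covariates or strata, and the shell of Table 18 holds only counts and percentages. SAP 8.4 carries the tests into the subgroups, for example for patients "whose absolute walking distance at 3 months improved by 100 metres or more from baseline using a chi-square test", and promises a forest plot of all subgroup analyses.

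The design and the primary model do use the omitted factors. SAP 5.9: "Randomisation will be blocked with random block sizes and stratified by centre". SAP 8.2, on the Tobit model: "The model will include the measurements of AWD baseline, treatment indicator, centre indicator and group indicator as covariates".

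On the cap, SAP 7.3 says that for a follow-up AWD "with a value equal to or greater than 790 metres the value will then be censored at 790m". At baseline, a patient who "walked more than 15 minutes during the study assessment (at baseline) the patient will be removed from the analysis". No rule says how to classify response when baseline lies close to the cap.

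**The concern.** A patient's chance of gaining 60 m or 100 m plausibly depends on the starting distance and on whether supervised exercise is part of care. Comparing crude proportions leaves that variation in the error. When allocation is balanced within strata that predict outcome, a test that ignores them tends to be conservative and to lose power.

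The second problem does not depend on power. A chi-square test gives a p-value. It does not give the difference that SAP 8.2 promises, or the estimates and intervals that a forest plot needs. The responder result therefore cannot be read alongside the adjusted primary estimate.

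The cap adds a small oddity: a patient who starts close enough to 790 m cannot be a responder whatever the treatment does.

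**Working it through.** **1. The plan's own figure.** Inputs from SAP 5.7: difference 60 m, SD 120 m, two-sided alpha 0.05, power 90%.

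n per arm = 2 × (1.960 + 1.282)² × 120² / 60² = 84.1, so 85 by the normal formula. The two-sample t calculation gives 86 (power 90.3%; 85 gives 89.99%). Total 172; 172 / 0.9 = 191.1, so 192. The plan's figure is reproduced. The documents give no power or response rates for the responder outcomes.

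**2. Response rates these figures imply.** Assumptions: baseline also has mean 200 m and SD 120 m, controls do not change on average, and r is the correlation between baseline and 3 months (not in the documents). The SD of change is 120 × √(2(1 − r)).

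- r = 0.5: SD of change 120 m. Control response = P(Z > 60/120) = 30.9%; treated response 50.0%. With 86 per arm, chi-square power = Φ[(0.191 − 1.96 × 0.0748) / 0.0734] = 73%.
- r = 0.7: SD of change 93 m. Responses 25.9% and 50.0%; power 91%.

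**3. Power with and without adjustment.** Simulation: 86 per arm, 12 centre strata, 60 m effect, 60 m threshold, cap 790 m, normal baseline, 1,000 trials per row. The SET effect and the centre SD are assumptions.

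| r | SET effect / centre SD (m) | Chi-square | Logistic: baseline + SET | Loss (points) | Centre-stratified CMH |
|---|---|---|---|---|---|
| 0.5 | 0 / 0 | 75.7% | 82.6% | 6.9 | 75.1% |
| 0.5 | 60 / 30 | 73.4% | 78.4% | 5.0 | 74.1% |
| 0.7 | 0 / 0 | 90.9% | 92.7% | 1.8 | 90.8% |
| 0.7 | 60 / 30 | 89.1% | 91.7% | 2.6 | 90.7% |
| 0.85 | 0 / 0 | 99.6% | 99.6% | 0.0 | 99.6% |
| 0.85 | 60 / 30 | 98.6% | 99.3% | 0.7 | 99.0% |

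The loss is about 0 to 7 points. Stratifying by centre alone moves power by about −1 to +2 points, so most of the gain comes from baseline AWD. A lognormal baseline with the same mean and SD gives losses of 0 to 5 points. At the 100 m threshold (r = 0.7, 60 / 30) power is 88.8% against 91.4%.

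**4. Type I error** (no treatment effect, r = 0.7, 3,000 trials; Monte Carlo standard error √(0.05 × 0.95 / 3000) = 0.4 points). The first figure is without SET and centre effects, the second with them.

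- Chi-square: 5.6%, 4.0%
- Logistic, baseline + SET: 5.7%, 5.2%
- Logistic, baseline + 11 centre dummies: 6.7%, 6.6%
- Centre-stratified CMH: 5.4%, 5.2%

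The chi-square does not inflate error. A full set of centre dummies does so slightly.

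**5. The cap.** A 60 m gain is impossible above 790 − 60 = 730 m at baseline, and a 100 m gain above 790 − 100 = 690 m. Baselines up to 15 minutes stay in, which is 800 m at the 3.2 km/h of Protocol 5.4. With mean 200 m and SD 120 m applied to baseline by assumption, and baselines over 800 m excluded:

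- above 730 m: about 0% (normal) to 0.18% (lognormal), and 0.0018 × 172 = 0.3 patients;
- above 690 m: 0.002% to 0.33%, and 0.0033 × 172 = 0.6 patients.

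If baseline had mean 350 to 400 m and SD 200 m (not in the documents), the shares would be 1.6% to 2.8% (3 to 5 of 172) and 2.8% to 5.3% (5 to 9 of 172).

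**The case against.** The case for leaving the plan alone is substantial. The responder test only supports the primary analysis. Baseline AWD is not absent from it, because the outcome is a change from baseline; it is missing only as a covariate. SET and exercise-advice patients are also compared separately, since SAP 8.4 and Table 2 repeat the test within each. The randomised test is valid. Patients near the cap are identified by a pre-randomisation value, so they fall in both arms by chance, and the Tobit model deals with the cap in the primary analysis.

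All of this stands, and it keeps the point small. It does not supply a pooled adjusted comparison or the promised estimate.

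In the other direction, a reader might infer a loss of some 20 points. Protocol 1.4 cites an average improvement of about 180 m with SET. Setting the SET gain at 180 m, the advice gain at 0 and the residual SD at 80 m gives 62% against 84%. That scenario does not fit the plan. With a baseline of 200 m, SD 120 m and slope 0.7, the control mean becomes 200 + (180 + 0)/2 = 290 m. The control SD becomes √(84² + 80² + 90²) = 147 m before the cap, and 143 to 144 m as simulated. SAP 5.7 assumes 200 m and 120 m. Protocol 8.1 cites 3-month improvements of 75 to 90 m. With a SET gain in that range, advice gain 0 and the same residual SD, the control SD is 119 to 121 m and power is 90-94% against 95-96%. A version matched on both moments (mean 201 m, SD 117 m) gives 91% against 95%.

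A reader might also take these tests to be the only analyses tied to the 60 m difference. They are not: in Protocol 8.1 and SAP 5.7, 60 m is a between-arm difference in mean AWD, which the primary model estimates.

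**Conclusion.** The point holds as an efficiency and reporting weakness in a supportive secondary analysis. The power cost is about 0 to 7 points near the plan's mean and SD: largest at a baseline correlation of 0.5 and close to nil at 0.85. It would be larger only if SET and advice gains differed by far more than an SD of 120 m allows. The correlation, the SET and centre effects and the baseline distribution are assumptions, because the documents give none of them.

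The missing effect estimate needs no assumption: it follows from the SAP text and the Table 18 shell.

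The validity finding covers the randomised comparison. It does not extend to subgroup analyses 4 and 5 in SAP 6.3, which compare SET with non-SET patients and so are not randomised contrasts.

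The cap affects fewer than 1 of 172 patients under the plan's mean and SD. The primary analysis and its conclusion are untouched.

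**What to change.** In SAP 8.2, 8.4 and Table 2, replace each responder chi-square with a logistic regression on treatment, baseline AWD and SET group. Handle centre by a random effect or by pooling small centres, not by a full set of dummies. Report the adjusted odds ratio and the marginal risk difference, each with a 95% confidence interval, and add these to the Table 18 and 19 shells and the forest plot. Keep the crude proportions as description.

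Within the SET or the non-SET group the SET term is constant and drops out. In subgroup analyses 4 and 5 it coincides with the contrast, so it cannot be a covariate; adjust for baseline AWD and label those results non-randomised.

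State how patients with baseline above 730 m (or 690 m) are classified. At most, add a sensitivity run without them. While the text is open, settle the threshold: SAP 8.2 counts gains at or above 60 m and 100 m, but the titles of Tables 18 to 21 count only gains above them.

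The cost is SAP wording and code. The model uses covariates already in the primary analysis and needs no new data.

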### 5.7 Sample Size

Assuming that the mean AWD in the control group is 200m at 3 months [5] and a common equal standard deviation of 120m [6], without considering the dropout rate, it is estimated that a sample size of 172 participants (86 per group) will have 90% power with a two-sided alpha = 0.05 to detect a difference of 60m in the mean absolute walking distance at 3 months between the intervention and the control group.

Assuming a 10% dropout rate, the sample size required for this study is 192 participants; 96 in each arm.

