	
 
• Proportion of patients whose absolute walking distance at 3 months improved by 60 metres or more from baseline
 
• Proportions of patients whose absolute walking distance at 3 months improved by 100 metres or more from baseline
 
	Chi-square test at 3 months
	Investigate if NMES+EA has similar effect as SET+EA, at 3 months	Chi-square test at 3 months
	Subgroup analysis 4: NMES+EA vs SET +EA	Tobit Regression for absolute walking distance at 3 months with AWD at baseline, Treatment, Centre and Group as covariates.
	Proportion of patients whose absolute walking distance at 3 months improved by 60 metres or more from baseline	Chi-square test at 3 months
	Proportions of patients whose absolute walking distance at 3 months improved by 100 metres or more from baseline	Chi-square test at 3 months
	To determine if NMES+SET+EA is more effective than NMES+EA, at 3 months.	Tobit Regression for absolute walking distance at 3 months with AWD at baseline, Treatment, Centre and Group as covariates.
	Subgroup analysis 5: NMES+SET+EA vs NMES+EA	Chi-square test at 3 months
	Proportion of patients whose absolute walking distance at 3 months improved by 60 metres or more from baseline	Chi-square test at 3 months
	Proportions of patients whose absolute walking distance at 3 months improved by 100 metres or more from baseline	Chi-square test at 3 months

\*\*Primary outcome

T Mechanistic outcome

Summaries of continuous variables will be presented as mean and standard deviations if normally distributed, and as medians and inter-quartile ranges for skewed data. Categorical variables will be presented as frequencies and percentages in the form of summary tables.

All statistical tests will be two-tailed with a 5% significance level.

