### **8.3 Secondary End Points Analysis**

#### **8.3.1 Continuous Secondary End Point Analysis**

The continuous variables of initial claudication distance (ICD), measured at baseline, 3, 6, and 12 months will be analysed using a Multilevel Tobit model fitted to the censored ICD measurements. The Multilevel Tobit models will be performed to investigate the effect of the treatment indicator on the changes over time (3, 6, and 12 months), treating patient as a random effect, while the baseline measurement of the continuous ICD variable, treatment, time, interaction of time\*treatment, centre, group (SET vs non-SET), age, gender and BMI will be treated as covariates. Results of the Multilevel Tobit model will be presented (see Table 24 Section 8.9.6.1).

A summary table of proportion of patients who increased the ICD both by more than 60 and by more than 100 metres by treatment and by visit will be presented (Table 25 and Table 26)

The secondary end points concerned with quality of life scores (QoL) measured at baseline, 3, 6 and 12 months, will be analysed using separate ANCOVA models for each outcome variable. The measurements of quality of life are the Intermittent Claudication Questionnaire (ICQ), EuroQoL 5D 5L (EQ-5D-5L) and the SF-36.

The ANCOVA models of each of the QoL scores will be performed to investigate changes in QoL over time and to assess the difference between the two treatment groups, while controlling for the baseline measurement of the QoL score being analysed. Results of the ANCOVA models will be presented in tables (see Section 8.9.6.2).

All individual scores for ICQ, EuroQoL 5D 5L and the SF-36 will be presented as Plots. Plots of the mean QoL scores will be used to illustrate changes over time by treatment arm (Figure 1-3, Section 8.10).

Duplex ultrasonography (DU) measurements (Mean Volume Flow and Mean Time Average Mean Velocity) from the Haemodynamic assessment will be analysed using separate linear regression models. The linear regression models will be used to compare the Mean Volume Flow (VF) and Mean Time Average Mean Velocity (TAMV)

Imperial Clinical Trials Unit	STATISTICAL ANALYSIS PLAN	NESIC
-------------------------------	---------------------------	-------

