**Table 20 Summary of Proportion of Patients that improved AWD by more than 60 m by visit and by treatment**

Visit	Improvement of >60 m in the AWD	NMES + Local available	Local available	Total
		Exercise therapy N=(XX)	Exercises therapy N=(XX)	
Baseline	Yes	XX (XX.X%)	XX (XX.X%)	XX (XX.X%)
	No	XX (XX.X%)	XX (XX.X%)	XX (XX.X%)
3 months	Yes	XX (XX.X%)	XX (XX.X%)	XX (XX.X%)
	No	XX (XX.X%)	XX (XX.X%)	XX (XX.X%)
6 months	Yes	XX (XX.X%)	XX (XX.X%)	XX (XX.X%)
	No	XX (XX.X%)	XX (XX.X%)	XX (XX.X%)
12 months	Yes	XX (XX.X%)	XX (XX.X%)	XX (XX.X%)
	No	XX (XX.X%)	XX (XX.X%)	XX (XX.X%)

**Table 21 Summary of Proportion of Patients that improved AWD by more than 100 m by visit and by treatment.** Same display as Table 20, but for improvement of AWD by more than 100 m

**Table 22 Output of Multilevel Tobit model to assess the effects of baseline characteristics for AWD at 3,6, and 12 months**

Fixed Part	Coefficient	SE	z	P> z	95% Confidence interval
AWD(Baseline)	XX.XX	XX.XX	X.XX	X.XXX	X.XX
Treatment	XX.XX	XX.XX	X.XX	X.XXX	X.XX
Time	XX.XX	XX.XX	X.XX	X.XXX	X.XX
Treatment *Time	XX.XX	XX.XX	X.XX	X.XXX	X.XX
Centre	XX.XX	XX.XX	X.XX	X.XXX	X.XX
Group	XX.XX	XX.XX	X.XX	X.XXX	X.XX
Age	XX.XX	XX.XX	X.XX	X.XXX	X.XX
Gender	XX.XX	XX.XX	X.XX	X.XXX	X.XX
BMI	XX.XX	XX.XX	X.XX	X.XXX	X.XX
Smoking status	XX.XX	XX.XX	X.XX	X.XXX	X.XX
_cons	XX.XX	XX.XX	X.XX	X.XXX	X.XX

Random part	Estimate	SE	95% Confidence interval
Between variance	XX.XX	XX.XX	X.XX
Within variance	XX.XX	XX.XX	X.XX

Number of obs = XX, Uncensored = XX, Left-censored= XX, Right-censored = XX

Multilevel Tobit model: Absolute Walking distance (3,6 and 12 months) = intercept + AWD(Baseline) + Treatment + Time + Treatment \*Time + Centre + Group + Age +Gender +BMI +Smoking Status + residual error. Treatment=NMES + local available exercise therapy vs. local available exercise therapy only (1,0), time= variable indicator, one for each follow up period (3 months, 6 months, 12 months) or treat it as time variable, Treatment\*time: Interaction term between treatment and time, Centre=centre identifier, Group= Set or non-SET group (1,0) and Baseline characteristics= Age, gender, BMI, Smoking status.

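### The secondary multilevel Tobit models for AWD and ICD assume one variance and one correlation over months 3, 6 and 12; if correlation decays, the one-coefficient test of change in effect from month 3 to 12 can run at about 7–11% instead of 5%

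*SAP*

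**What the plan says.** - **AWD.** SAP 8.2 states: "A Multilevel Tobit model will be used to investigate the difference in absolute walking distance between the two treatment groups". It covers months 3, 6 and 12, with time, treatment and their interaction in the model and adjustment for baseline AWD. SAP Table 2 adds that patient is a random effect.
- **ICD.** SAP 8.3.1 plans the same type of model, "treating patient as a random effect, while the baseline measurement of the continuous ICD variable" is a covariate.
- **Covariance.** The random part of Table 22 has two rows, "Between variance" and its within-patient counterpart. Table 24 has the same two. The model equations add a single residual term. Neither document mentions a random slope, serial correlation, visit-specific variance or robust standard errors.
- **Test.** Both tables report the Treatment*Time row with a z and a p-value, which is a single-coefficient Wald test. The table notes leave open whether time is a set of visit indicators or one time variable.
- **Error rate.** SAP section 8 states: "All statistical tests will be two-tailed with a 5% significance level".
- **Other tests beyond month 3.** None is planned for AWD or ICD. The AWD chi-square tests are at 3 months, and Tables 20, 21, 25 and 26 are descriptive. For ICD this model is the only planned test at any visit.

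**The concern.** A patient random intercept with one residual variance forces the same SD at every visit and the same correlation between any two visits. The schedule makes that doubtful. The visits are 3 and then 6 months apart, and device treatment ends at month 3. Walking distances at months 3 and 12 may well be less alike than those at months 3 and 6.

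If so, the model applies an average correlation to every pair of visits. It understates the variance of the 12-versus-3-month comparison and overstates that of the 6-versus-3-month comparison. At stake is what the trial says about months 6 and 12: a claim that the device effect fades, holds or grows could rest on a p-value whose true error rate is above the stated 5%.

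**Working it through.** **The plan's own figures.** SAP 5.7 says "a sample size of 172 participants (86 per group) will have 90% power" "to detect a difference of 60m in the mean absolute walking distance at 3 months", with "a common equal standard deviation of 120m". The normal approximation gives 2 × (1.96 + 1.2816)² × (120/60)² = 84.06, so 85 per arm. The t-based solution is 85.03, so 86, with power 0.903. Then 172/0.9 = 191.1, so 192. These figures reproduce. They concern month 3 only; nothing in the documents describes the later visits' SDs or correlations.

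**Censoring.** With means of 200 and 260 m and SD 120 m, the chance of exceeding 790 m is about 4 × 10⁻⁷ and 5 × 10⁻⁶. On these inputs the Tobit behaves like a linear mixed model, so closed forms apply.

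**Formula.** With complete data and visit indicators, the random-intercept model uses the average variance v and average covariance c over the three visits. For a contrast a with true covariance V:

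ratio = a′Va / [a′(model covariance)a], and size = 2 × [1 − Φ(1.96/√ratio)].

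With equal SDs, the 12-versus-3 ratio is (1 − r₃,₁₂)/(1 − mean r) and the 6-versus-3 ratio is (1 − r₃,₆)/(1 − mean r).

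**Equal SDs, assumed correlations**

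| r(3,6) / r(6,12) / r(3,12) | 12 v 3 ratio | 12 v 3 size | 6 v 3 ratio | 6 v 3 size |
|---|---|---|---|---|
| .70/.70/.70 | 1.00 | 5.0% | 1.00 | 5.0% |
| .75/.70/.65 | .35/.30 = 1.17 | 7.0% | .25/.30 = 0.83 | 3.2% |
| .80/.70/.60 | .40/.30 = 1.33 | 9.0% | .20/.30 = 0.67 | 1.6% |
| .80/.70/.50 | .50/.333 = 1.50 | 11.0% | .20/.333 = 0.60 | 1.1% |

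Simulation of the three decaying patterns (20,000 trials each, 86 per arm) gave 7.1%, 9.4% and 11.4% for 12 versus 3.

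**Linear time.** The centred weights for months 3, 6 and 12 are −4, −1 and 5. For .80/.70/.60 the ratio is [42 + 2(3.2 − 3.5 − 12)]/(42 × 0.30) = 17.4/12.6 = 1.38, so the size is 9.5%.

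**Range of assumed truths.**
- Correlation of 0.5 to 0.9 per 3 months with geometric decay: 7.8–10.4% (12 v 3) and 8.5–11.2% (linear time).
- A permanent patient effect plus a decaying part plus measurement error: 6.9–7.9%.
- A random slope with SD 0.02–0.06 per month, in units of the outcome SD: 5.3–7.2% (12 v 3).
- The joint two-degree-of-freedom interaction test across the patterns examined: about 5–7%.

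**Fitted multilevel Tobit, censored at 790 m** (1,500 runs, simulation error about 0.7 points). At 0.7 per 3 months: 8.6% (12 v 3) and 9.3% (linear). At 0.8: 9.9% and 10.7%. At 0.8 with about 4% censored: 10.2% and 10.0%. At constant correlation: 5.7% and 5.4%.

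**The 12-month and 3-month effects.** Here the ratio is the visit's residual variance over the average. With constant residual variance it is 1, and the size is 5%. Residual variance can grow in two ways:

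1. *The SD rises.* Take 120/135/150 m (assumed). The variances are 14,400, 18,225 and 22,500, with mean 18,375. Month 12: 22,500/18,375 = 1.22, size 7.7%. Month 3: 14,400/18,375 = 0.78, size 2.7%.
2. *Baseline predicts month 12 less well than month 3.* Take correlation 0.8 per 3 months and equal SDs. The baseline correlations are .80, .64 and .41, so the common slope is their mean, .6165. Residual variances 1 − 2 × slope × r + slope² are .394, .591 and .875, with mean .620. Month 12: ratio 1.41, size 9.9%. Month 3: ratio 0.635, size 1.4%. Simulation (4,000 runs) over 0.7 to 0.9 per 3 months gave 8.8–11.8% at month 12 and 0.8–2.2% at month 3.

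**After the fix** (12 v 3, correlations 0.6 and 0.8 per 3 months)

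| Data | Random intercept | Patient-clustered robust SE | Unstructured covariance |
|---|---|---|---|
| Complete, 86 per arm | 8.5%, 9.5% | 5.7%, 4.8% | 5.7%, 4.8% |
| 10/20/30% missing, 96 per arm | 7.3%, 8.9% | 4.8%, 5.1% | 5.1%, 5.0% |

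These runs used a linear random-intercept model.

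**The case against.** The strongest reply is that every inflated figure depends on correlations or SDs that the documents do not give. Under constant correlation and variance the planned model is correct. That stands, and the finding is therefore conditional.

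Four further points have weight:

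- For AWD, 8.2 names the treatment difference at 3, 6 and 12 months as the target. Persistence can fairly be read as the 12-month difference, not the interaction, and that difference is inflated only if residual variance grows.
- This is a secondary analysis. Protocol 8.3 introduces the repeated-measures model as a way to study baseline variables such as BMI, and Table 22's title says the same. No rule ties a durability claim to it.
- The SAP does not say that standard errors are model-based. The table layout would also fit robust ones, so this is an unspecified choice whose usual default is the problem.
- Pandemic disruption mainly implies missing treadmill tests, because the test needs an on-site visit. It does not by itself imply a changed covariance.

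A reader might infer that the models' error rate is simply not 5%, or that the 12-month interval is always too narrow and the 3-month one always too wide. The documents support neither: both need a covariance pattern that they do not state, and some contrasts become conservative. What the reply does not remove is that these are the only planned tests of AWD and ICD beyond month 3, and that the reported form is the single-coefficient test that is sensitive.

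**Conclusion.** The point holds in conditional form. The covariance restriction is read directly from Tables 22 and 24. If correlation falls as the gap between visits grows, the 12-versus-3-month or linear-time interaction test can run at about 7–11%. Mild departures give less, and missing data reduced the inflation somewhat (7.3–8.9%). The 6-versus-3-month contrast errs the other way. The 12-month effect is inflated, and the 3-month effect conservative, only with growing residual variance.

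It would be wrong to infer that the primary result is at risk: the primary analysis is a separate single-visit Tobit regression at 3 months. The change is worth making before later results are seen because it is cheap and these models carry the inference on later walking distance.

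**What to change.** In SAP 8.2 and 8.3.1, and in the notes to Tables 22 and 24:

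1. State that the multilevel Tobit models use robust standard errors clustered on patient. Alternatively, specify a visit covariance that allows both unequal variances and decaying correlation. Visit-specific residual variance alone is not enough, because it does not let correlation decay with the gap.
2. Code time as visit indicators and delete the option of a single time variable.
3. Name the contrast that answers persistence: the 12-month treatment difference, the 12-versus-3-month interaction, or both.

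The cost is one model option and a few sentences. Some intervals become slightly wider. With about 170–190 patients as clusters, the robust variance should be reliable. Robust standard errors do not remove bias in the estimates if censoring or missingness is substantial; on the plan's 200/260/120 m figures, censoring is negligible.
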